Exclusion criteria to participation in this study include:

- 5) Age < 18
- 6) Emergency surgery
- 7) Persons not capable of providing informed consent
- 8) Persons participating in any other research study involving an investigational drug or device or investigational surgical procedure that could interfere with the physiologic parameters being collected (for example, a study evaluating different anesthesia regimens that could confound study results).
- 9) Non English-speaking

2.2 - Hypothesis

It is hypothesized that the AirSeal® System will allow for lower CO₂ absorption rates than the Xcel® System. Furthermore, lower variance in pneumoperitoneal pressure will allow for less "over-pressure" events and peritoneal stretch, which may reduce postoperative pain. Pain will therefore also be assessed through self-report and post-operative pain medication usage (see Table 4 & Appendix A), and analyzed in comparison between both groups.

The term "over pressure" refers to times when the measured pressure in the peritoneal cavity exceeds the set pressure on the insufflator. In such cases, the standard insufflation systems will stop the flow of CO₂ into the abdomen through the port and will actively vent gas to reduce the pressure back to the set point (usually 10mmHg with a maximum of 20mmHg). This "over pressure" theoretically should not occur with the AirSeal® system because the lack of a valve on the port allows gas to escape immediately when the pressure rises (e.g. abdominal muscle contractions when anesthesia is light) so that the pressure does not exceed the set level. "Peritoneal stretch" refers to stretching of the peritoneum (lining of the abdominal wall) from insufflation of the abdomen. The higher the pressure of the pneumoperitoneum/intra-abdominal pressure, the more stretch there will be of the peritoneum with potentially more postoperative pain.

We intend to analyze the results of a total of 100 patients randomized to either the AirSeal® system or conventional trocars.

2.3 - Study Variables & Outcomes of Interest

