- 9) Insufflation pressure at which the procedure was performed (mmHg), and the total number (#), magnitude(s) (% increase in mmHg), and time(s) (hh:mm) of increased pressure episodes necessary to successfully complete the procedure
- 10) Procedure time (minutes from initial incision to closure)
- 11) Pneumoperitoneal pressure ranges (mmHg)**

12) Smoke evacuation quality at the end of surgery (1-Below Average; 2-Average Amount; 3-Above Average) (Appendix B)
 
13) Number of times significant loss of pneumoperitoneum occurs (#), timepoint, and level of pressure adjustment (mmHg)
 
14) Scope cleanings (#)
 
15) Malfunctions of the AirSeal® System or control devices (# times)
 
16) Total amount of gas used during the procedure (liters)

(c) Postoperative data collected in the PACU through discharge:
 
1) Postoperative pain by the NRS-11 at multiple time points (Appendix A)
 
2) Postoperative parameters (as recorded by the PACU nurses as standard of care)
 
a) O₂ saturation (%)
 
b) Time in PACU (post anesthesia care unit) (hours)
 
c) Post-operative nausea and vomiting (presence/absence)
 
d) Vital signs (HR/RR/BP/temp) – first recorded in PACU setting
 
e) Use of post-operative pain medication (ketorolac, Percocet, Tylenol Extra Strength), recorded as the total daily morphine equivalent dose (“MED”, in mg/day)
 
3) Incidence of wound infection
 
4) Length of stay (targeting same day or next day discharge; 0 to 2)

(d) Postoperative data collected through postoperative Day 1
 
1) Postoperative parameters (standard of care)
 
a) Vital signs (HR/RR/BP/temp) – first recorded in non-PACU setting
 
b) Use of post-operative pain medication (ketorolac, Percocet, Tylenol Extra Strength), recorded as the total daily morphine equivalent dose (“MED”, in mg/day)
 
2) Serum creatinine (mg/dl)
 
3) Hemoglobin (g/dl)
 
4) Urine output (ml; 1900-0700 hours postoperatively)
 
5) Incidence of wound infection

For item (b)2, a deviation from the standard port number/size(s)/locations would be due to body habitus, and will not have an effect the clinical outcomes for the patient. We will collect information on all surgical outcomes that occur until discharge from the PACU. The average amount of time spent in the PACU is roughly 1-2 hours. There will be no extended or long-term follow-up.

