Recruitment will occur either at the preoperative office/clinic visit, in the office setting, or in the pre-anesthesia testing office visit (PAT). The study will be explained to the potential subject with ample opportunity to ask questions and consider participation. Recruitment will occur prior to administration of any narcotic or sedative medications. Each potential subject will provide written informed consent prior to any research-related procedure, recording/documenting, or activity occurring. An individual's consent to participate will be documented on the IRB-approved informed consent form. The original executed consent form will be retained in the Principal Investigator's study files; a copy will be given to the subject to retain. The original copy will be kept in a locked cabinet along with all study documents that contain private subject information.

Following informed consent, patients will be randomized and prepared for surgery per standard institutional policy and practice. Prior to the start of the study, the study site will set up a computer based randomization system that will randomize subjects into either one of the two groups. Based on the randomization sequence, either the AirSeal® System or a conventional insufflator and trocar will be inserted per the surgeon's normal operative procedures and care (i.e., Endopath® port with standard insufflation). A total of one AirSeal® Access Port will be used on any one subject. For every control subject, one 5mm or larger port used will be designated and recorded as the "study" port. [name] will be the only surgeon performing these procedures, eliminating variation in technique between surgeons. The AirSeal® port is 5mm in size and the standard insufflation port is 12mm in size, so the study population will not be subjected to larger port sizes than they would if off-study.

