As stated earlier, if a technical malfunction of the AirSeal® iFS or AirSeal® Access Port were to occur, the surgeon will replace both with a conventional insufflator and trocar. This is the same procedure that would take place should a technical malfunction occur with conventional insufflator and trocar. If the surgeon decides that the operation is not feasible with a standard insufflator and trocar (loss of insufflation/inconstant pressure with bleeding or anesthesia problems), then the surgeon can replace the standard insufflators with the AirSeal® iFS or AirSeal® Access Port. These events will be documented should they occur.

Patients will undergo standard insufflation (filling of the peritoneal cavity with CO₂ gas). After trocar placement, initial insufflation will be performed to 6mmHg in all patients. All procedures will be performed as per standard technique. If required, insufflation pressures will be increased up to 15mmHg per standard surgeon protocol. Increased insufflation pressure will be maintained either transiently (\leq 5 minutes to control bleeding or to improve access/visualization) or for the duration of the procedure as per surgeon need. The amount of time at each insufflation pressure will be measured. Procedures in which $<5\%$ of the case are performed above 8mmHg will be considered "low impact" procedures. We will compare CO₂ absorption rates between high pressure (>8mmHg) and low impact (\leq 8mmHg) procedures in the final analysis.

Study subjects will also be removed from the study if they revoke their informed consent. If, in the opinion of the surgeon/investigator, clinical observations made during the study suggest it may be unwise to continue, the surgeon/investigator may stop the study. In the event that the investigator chooses to discontinue or terminate the study, appropriate notification will be given to the IRB and sponsor.

The principal investigator also has the right to remove any subject from the study. Reasons for which a subject may be removed from the study include:

- Occurrence of a serious or intolerable adverse event
- The subject requests to be discontinued from the study
- Non-compliance with medication, protocol violation or unreliable behavior
- A protocol violation sufficiently serious as to require subject withdrawal
- Emergence of a clinically significant change in a laboratory parameter(s)

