- General or specific changes in the subject's condition that render further treatment unreasonable or unsafe within the standards of clinical practice in the judgment of the Principal Investigator or treating physician

2.5 – Statistical Analysis

We will first compare the demographic and pre-operative clinical characteristics of the conventional and valve-less trocar groups to evaluate randomization fidelity. If any characteristics are found to be statistically significant between the groups, this will be accounted for in the analyses of the primary and secondary outcomes. We will describe all categorical variables as percentages and continuous variables with means and standard deviations.

Aim #1) Describe the perioperative CO₂ absorption rates between the conventional and valve-less trocar groups via the end-tidal CO₂ and PaCO₂ , at baseline, 60 minutes intraoperatively, and immediately following surgery. We will also examine the valve and valve-less trocar groups on their ability to maintain acceptable ABG levels by comparing the number of interventions required by the anesthesiologist during the procedure between groups.

We will describe the change in CO₂ and PaCO₂ levels at 3 intervals: baseline to 60 minutes, 60 minutes to end of surgery, and baseline to end of surgery to examine the trends in both groups. We will compare the conventional and valve-less trocar groups on the number of interventions required by the anesthesiologist to maintain acceptable pressure using Poisson regression. If a significant number of patients required no intervention we will use a zero-inflated model. Statistical significance will be set at p<.05. We will also compare CO₂ absorption rates between high pressure (>8mmHg) and low impact (≤8mmHg) procedures.

Aim #2) Compare the maximum pneumoperitoneal pressure (mmHg), smoke evacuation quality (categorical), and overall operative times (minutes) between the conventional and valve-less trocar groups.

We will compare the conventional and valve-less trocar groups on maximum pneumoperitoneal pressure and overall operative time using t-tests or Wilcoxon rank sum tests. We will compare the groups on evacuation quality using a chi-square test. Statistical significance will be set at p<.05.

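### Section 2.2 hypothesises less over-pressure, defined relative to set pressure, but the only between-arm pressure test in 2.5 is absolute maximum pressure, which cannot separate the two

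*Combined protocol and SAP*

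**What the plan says.** **Hypothesis (section 2.2).** Less over-pressure is expected with AirSeal. The term "refers to times when the measured pressure in the peritoneal cavity exceeds the set pressure on the insufflator". With AirSeal, gas should escape at once "so that the pressure does not exceed the set level". The same section links peritoneal stretch to the absolute level: "The higher the pressure of the pneumoperitoneum/intra-abdominal pressure, the more stretch there will be of the peritoneum with potentially more postoperative pain".

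**Conduct (section 2.4).** All cases start at 6 mmHg. After that, "If required, insufflation pressures will be increased up to 15mmHg per standard surgeon protocol", either briefly or for the whole case. One surgeon "will be the only surgeon performing these procedures". The study is single-blind and the blinded party is not named; the surgeon places the port and so presumably knows the arm.

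**Data.** Section 2.4 adds: "The amount of time at each insufflation pressure will be measured". Table 2(b)9 in section 2.3 records operating pressure and the number, size and times "of increased pressure episodes necessary to successfully complete the procedure", which reads as deliberate rises. Table 2(b)11 records pressure ranges. The forms in Appendices C and D are not visible.

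**Analysis (section 2.5, Aim 2).** "We will compare the conventional and valve-less trocar groups on maximum pneumoperitoneal pressure and overall operative time using t-tests or Wilcoxon rank sum tests".

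**The concern.** The hypothesis concerns excess over the set point, while the test concerns the absolute peak. The peak equals the set pressure at that moment plus any excess, and the set pressure is chosen after randomisation, so randomisation does not by itself equalise it. An AirSeal case raised to 15 mmHg with no spike and a control case at 8 mmHg with a 7 mmHg spike both score 15.

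Interpretation is what is at stake. If set pressures differ by arm, a significant Aim 2 result could reflect how often the surgeon raised pressure, and a null could hide a real reduction in spikes. If set pressures match, the test keeps its 5% error rate, and variation in set pressure costs only power. In neither case does the plan examine over-pressure, although the protocol rests part of the device's rationale on it.

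**Working it through.** **1. Does anything else in 2.5 fill the gap?**
- The Poisson model mentions keeping pressure acceptable, but section 1.2 and Table 2(b)5 show that it counts ventilation adjustments made for CO₂.
- The high-pressure versus low-impact comparison has CO₂ absorption as its outcome.
- The adjustment rule for group imbalance covers demographic and pre-operative characteristics. Set pressure is intraoperative.
- Continuous variables are to be described by means and SDs, which could include operating pressure, but reporting by arm is not explicitly promised.

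So no between-arm analysis of over-pressure is planned. The documents give no power figure for this comparison, so there is none to reproduce.

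**2. Inputs for an illustration.** From the documents: 100 patients in total, a start at 6 mmHg, a ceiling of 15 mmHg, p<.05. Assumed: 50 per arm, two-sided tests, escalation rates and excess sizes. Rises go either to 15 mmHg (h = 9, the widest split that 2.4 allows) or to 10 mmHg (h = 4).

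Maximum = set pressure at the peak + excess, with excess cut off at 0. If a share p is raised by h, the variance of set pressure is h²p(1−p). For the t-test, approximately:

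power = Φ(|D|/SE − 1.96), SE = √[(V_AirSeal + V_control)/50]

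The simulated figures below used 20,000 trials per scenario.

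**3. True over-pressure benefit, equal escalation (50% in both arms).** Excess is N(2, SD 2) in control and N(0, SD 1) in AirSeal. After the cut at 0, the means are 2.17 and 0.40 and the variances 3.00 and 0.34, so D = 1.77 mmHg.
- Rises to 15: set variance 81 × 0.25 = 20.25; SE = √[(20.25 + 0.34 + 20.25 + 3.00)/50] = 0.936; 1.77/0.936 = 1.89; power 47%. Simulated: 46-47% (t-test), 80-82% (Wilcoxon).
- Rises to 10: set variance 16 × 0.25 = 4; SE = √[(4 + 0.34 + 4 + 3.00)/50] = 0.476; 1.77/0.476 = 3.72; power 96%. Simulated: 96% and 92%.
- Set pressure uniform over 6-15 mmHg, simulated: 86% and 80%.
- Measured minus set: SE = √[(0.34 + 3.00)/50] = 0.259; 1.77/0.259 = 6.8; power over 99%.

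**4. No over-pressure difference, unequal escalation.** Excess is N(3, SD 2) in both arms (variance 3.55 after the cut). With AirSeal 30% and control 50% raised to 15, D = 9 × 0.20 = 1.8; SE = √[(17.01 + 20.25 + 2 × 3.55)/50] = 0.942; 1.8/0.942 = 1.91; 48%. Simulated shares of significant results:

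| AirSeal escalation v control 50% | To 15: t / Wilcoxon | To 10: t / Wilcoxon |
|---|---|---|
| 40% | 15% / 14% | 11% / 12% |
| 30% | 47% / 41% | 31% / 32% |
| 20% | 84% / 74% | 62% / 62% |

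With equal escalation to 15 mmHg, the share is 5%.

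**5. True benefit, AirSeal raised more often (50% v 30%).** For rises to 15, D = 1.77 − 9 × 0.20 = −0.03, so the benefit cancels; simulated detection is 5% (t-test) or 19% (Wilcoxon). For rises to 10, D = 1.77 − 4 × 0.20 = 0.97; simulated 54% or 44%.

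**6. Limit of measured minus set.** In steps 3 to 5 excess does not depend on set pressure. Suppose that mean excess changes by 0.1, 0.2 or 0.3 mmHg per mmHg of set pressure, with no device effect and AirSeal 30% or 20% v control 50% raised to 15. Measured minus set is then significant in about 7-10%, 12-24% and 19-42% of trials. These slopes are also assumed.

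**The case against.** The plan tests what Aim 2 names. Over-pressure enters 2.2 as a supporting mechanism leading towards pain, and pain is tested in Aim 3. No conclusion rule depends on an over-pressure result. Section 2.2 ties stretch to absolute pressure, so the maximum is a sensible endpoint. If the port lets the surgeon raise pressure less often, a lower maximum is a real effect of assignment. All of this stands.

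A reader might therefore take the table in step 4 as false-positive rates for Aim 2. They are not. Those are true differences of 0.4 to 2.7 mmHg in the planned endpoint, and they mislead only if the result is labelled over-pressure, which 2.5 never does. Nor do the documents show that escalation will differ by arm. A difference is plausible, since better access or visualisation is one stated reason for a rise and the device is expected to affect smoke evacuation, but one surgeon works to one standard protocol.

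The lowest power also depends on settings of only 6 or 15 mmHg and on the t-test. Wilcoxon, which the plan allows, does much better there, and milder rises cost little. Finally, the unseen forms may already link measured and set pressure. That could remove the request on recording, but it would not add an analysis to 2.5.

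**Conclusion.** The concern holds as a gap in a secondary, mechanistic analysis, of minor to moderate weight. Followed exactly, section 2.5 gives a valid comparison of maximum pressure but cannot say whether the valve-less port reduced over-pressure as section 2.2 defines it.

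The practical size is unknown. Under the assumptions shown, and with equal escalation, the loss of power ranges from slight to about half. With unequal escalation, the maximum can differ without any over-pressure difference, or can hide one.

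Two further inferences are not supported. One is that the plan leaves set pressures unreported: 2.5 promises means and SDs, though not explicitly by arm. The other is that measured minus set would settle attribution: it does so only if excess does not vary with set pressure.

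**What to change.** - **Section 2.5, Aim 2.** Keep absolute maximum pressure as planned. Add a supporting between-arm comparison of the largest value per case of measured minus concurrent set pressure, under the same t-test or Wilcoxon rule.
- **Beside that result,** report maximum and time-weighted mean set pressure by arm, with the difference and its 95% interval.
- **Table 2(b)11.** Record the measured range for each set-pressure period, unless the Appendix C or D forms already do so. This should be settled before the first case, because ranges not linked to set pressure may not be recoverable later.
- **State the limit.** Excess over set may itself vary with set pressure. If set pressures differ by arm, the added comparison reduces the attribution problem without removing it.
- **Event counts.** Count over-pressure events only if the insufflator already logs pressure over time. The minute-by-minute export in section 2.3 lists ventilator and vital-sign variables, not abdominal pressure, and ranges cannot supply a count.

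The cost is some wording, modest extra intraoperative recording and one more supporting test at p<.05. Operating pressure, rises and their times, and time at each pressure are already to be collected. The surgeon's discretion and the existing endpoint do not change.

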A new class of valve-less trocars (i.e. the AirSeal® System) is seeking to replace the standard “trap door” valve and silicone valve trocars with a curtain of forced CO₂ gas that is collected, filtered, and then pumped back into the peritoneum to maintain the pressure differential.⁴ The AirSeal® System consists of an insufflation, filtration, and recirculation system (AirSeal® iFS), a triple lumen filtered tube set, and a valve free trocar (AirSeal® Access Port). The device enables peritoneal access with a novel mechanism to maintain pneumoperitoneum without a mechanical seal. Specifically, the AirSeal® System creates a pressure barrier within the proximal housing of the cannula which acts as an invisible seal to maintain pneumoperitoneum during the course of surgery. It utilizes a re-circulation and filtration control unit (AirSeal® iFS) designed specifically for the AirSeal® Access Port to create and maintain the pressure barrier. The AirSeal® iFS is reusable and the AirSeal® Access Port and triple lumen filtered tube set are designed as single patient use devices. The AirSeal® System has applications in minimally invasive abdominal surgical procedures to establish a path of entry for laparoscopic instruments. The lack of a physical valve allows the AirSeal® port to vent immediately in the event of any pressure spikes as the port has a constant opening where the pneumoperitoneal gas may escape to keep pressures down. The implications of this benefit on patient outcomes is not yet fully characterized.

1.2 – Specific Aims/Rationale

Since its FDA clearance, the AirSeal® system has been used routinely in centers throughout the United States, including OhioHealth Dublin Methodist Hospital. The AirSeal® system has been observed by surgeons and anesthesia teams to provide a more gentle, stable, and consistent pneumoperitoneum.⁵

In studies observing valve-less trocar use, patients had blunted end-tidal CO₂ levels and CO₂ absorption rates (see Table 1 for definitions) compared with those found in transperitoneal laparoscopies using the conventional trocar.^{6,7} The valve-less trocar has also been shown to eliminate stagnant surgical smoke as well as decrease operative time and CO₂ consumed.^{6,7} A prospective analysis of these values in a head-to-head comparison between valve-less and conventional trocars is desired.

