HCO ₃	Amount of bicarbonate in the arterial blood. This is used to aid in diagnosis of metabolic acidosis or alkalosis.	mmol/L
PaO ₂	Partial pressure of oxygen in the arterial blood. This is the true measure of O ₂ build in the blood.	mmHg
PaCO ₂	Partial pressure of carbon dioxide in the arterial blood. This is the true measure of CO ₂ build up in the blood, and reflects whether the lungs are keeping up in expelling the extra CO ₂ from abdominal absorption.	mmHg
End tidal CO ₂	The level of carbon dioxide in the air exhaled from the body, as measured by the ventilator. Essentially, this reflects the amount of CO ₂ that the lungs are expelling due to CO ₂ absorption from the insufflations. This increases over the course of the procedure.	mmHg
"Blunted" end tidal CO ₂	A technical observation made regarding the shape of the end tidal CO ₂ curve on the capnogram displayed on the ventilator. This is an observation, not discretely measureable.	N/A
Tidal volume	The lung volume representing the normal volume of air displaced between normal inspiration and expiration when extra effort is not applied (i.e., normal/resting breathing).	ml
O ₂ saturation	Measure of how much oxygen the blood is carrying as a percentage of the maximum it could carry.	%
Pneumoperitoneal pressure	Measurement of air or gas in the abdominal (peritoneal) cavity.	mmHg
Peak inspiratory pressure (PIP)	Point of maximal airway pressure.	mmHg
Positive end-expiratory pressure (PEEP)	Pressure maintained in airways at end of exhalation.	mmHg
Smoke evacuation quality	Smoke evacuation occurs during surgical procedures where there is tissue ablation. Smoke evacuation systems capture the plume (smoke comprised of carbonized cell fragments, water vapor, and hydrocarbons) from vaporized tissue near its origin before it becomes air-dispersed and deposits in the respiratory tracts of the surgical team.	Categorical (see Appendix B)

2.0 - METHODS

2.1 - Study Population

Adult male patients \geq 18 years of age with prostate cancer who are eligible and electing to undergo robotic prostatectomy surgery at OhioHealth Dublin Methodist Hospital between March 1, 2016 and February 28 2017 (12 months). Exclusion criteria to robotic surgery include:

- 1) Cirrhosis or liver failure (Child-Pugh class A, B, or C) or clinical suspicion of liver failure
- 2) Ascites
- 3) Uncontrolled diabetes [as reported by the pre-anesthesia testing (PAT) physician]

4) Renal insufficiency (serum creatinine level > 3.0 mg/dl)

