30 minutes post-operatively	30 minutes after surgical completion time (+/- 5 minutes)
60 minutes post-operatively	60 minutes after surgical completion time (+/- 5 minutes)
At discharge	Immediately prior to discharge from the PACU

B. Smoke Evacuation Quality Questionnaire

For surgeon completion post-operatively (circle one):

1-Below Average 2-Average Amount 3-Above Average

C. Data Collection Forms (see attached)

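### The ordered three-level smoke evacuation rating is tested with an unordered chi-square, which ignores the order and gives no directional estimate; an ordinal analysis is a cheap improvement with one named risk

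*Combined protocol and SAP*

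**What the plan says.** Smoke evacuation quality is one of three outcomes named under Aim #2 in sections 1.2 and 2.5, where it is described as categorical. The only test given for it in section 2.5 is "We will compare the groups on evacuation quality using a chi-square test", with "Statistical significance will be set at p<.05". No trend, rank or ordinal version is named, so the plain reading is a Pearson chi-square on a 2×3 table with 2 degrees of freedom. The same paragraph of section 2.5 offers t-tests or Wilcoxon rank-sum tests for the other two Aim #2 outcomes. Section 2.5 also says that categorical variables will be described as percentages.

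The surgeon circles one of three levels after the operation (Appendix B): "1-Below Average 2-Average Amount 3-Above Average". Table 2(b), item 12 in section 2.3 carries the same labels. Table 1 explains what smoke evacuation is but does not say which end of the scale is favourable.

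On the expected direction, section 1.2 states: "The valve-less trocar has also been shown to eliminate stagnant surgical smoke". Section 2.4 lists smoke evacuation among the potential benefits for patients allocated to AirSeal.

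**The concern.** Below, average and above form an order. A Pearson chi-square treats the three levels as interchangeable names: shuffling the columns leaves the statistic unchanged. It asks whether the two distributions differ in any way, and it returns a p-value with no estimate of which arm did better or by how much. If the effect is a general shift towards better ratings, spreading the test over 2 degrees of freedom costs power that an ordinal test would keep with the same 100 patients.

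A smaller matter is the middle label, which alone carries the word *amount* without saying of what. If a rater took it to mean the amount of smoke, the top category would be the worst one.

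**Working it through.** **Inputs from the documents.** Total of 100 patients (section 2.2); significance at 0.05 (section 2.5); three ordered levels (Appendix B). The available text gives no power calculation, effect size or expected rating distribution for this outcome, so there is no planned figure to reproduce.

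**Assumptions.** Equal allocation, 50 per arm (no ratio is stated); two-sided tests; the control-arm splits; the odds ratios; and a proportional-odds shift, unless another shape is given.

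**Step 1: what the chi-square ignores.** Take an illustrative table of 15/25/10 (control) against 8/23/19 (valve-less).
- Column totals are 23, 48 and 29, so the expected counts per arm are 11.5, 24 and 14.5.
- X² = Σ(O − E)²/E = 2 × (3.5²/11.5 + 1²/24 + 4.5²/14.5) = 2 × (1.065 + 0.042 + 1.397) = 5.01 on 2 df, p = 0.082. Reversing or shuffling the columns gives the same value.
- Tie-corrected Wilcoxon on the same table: p = 0.026.
- Probability that a valve-less rating exceeds a control rating, ties counted half: [19 × 40 + 23 × 15 + 0.5 × (8 × 15 + 23 × 25 + 19 × 10)] / 2500 = 1547.5/2500 = 0.62.
- Reversing the scale turns 0.62 into 0.38 and leaves both p-values unchanged. The label therefore affects interpretation, not the test.

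**Step 2: power under a proportional-odds shift.** For each cut-point, odds in the valve-less arm = OR × odds in the control arm. With control 25/50/25 and OR 2.5:
- P(level 2 or 3): odds 3 × 2.5 = 7.5, giving 0.882.
- P(level 3): odds 0.333 × 2.5 = 0.833, giving 0.455.
- The valve-less split is then 11.8/42.8/45.5, to rounding.

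Simulated power, chi-square → Wilcoxon:

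| Control split | OR 2 | OR 2.5 | OR 3 |
|---|---|---|---|
| 25/50/25 | 34.9% → 44.1% | 56.6% → 67.0% | 72.9% → 82.0% |
| 20/60/20 | 31.9% → 40.9% | 52.8% → 63.4% | 69.5% → 79.3% |
| 15/60/25 | 33% → 42% | 54% → 65% | 71% → 80% |

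The gain is about 9 to 11 points. At OR 4 it shrinks to 90.5% → 94.9% for 25/50/25 and 88.9% → 93.8% for 20/60/20. At OR 1.5 with 25/50/25 it is about 4 points. If ratings pile up in the middle (10/80/10), the gain is about 7 points at OR 2 (21.0% → 28.5%) and 9 at OR 4 (74.1% → 83.6%). Type I error is about 5% for both tests.

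**Step 3: cross-check.** For 80% power the noncentrality needed is 7.85 on 1 df and 9.63 on 2 df. The ratio is 9.63/7.85 = 1.23, so when the whole effect lies along the ordered direction the 2-df test needs about 23% more patients. At noncentrality 7.85 it has 70.9% power instead of 80%.

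**Step 4: shapes that favour the chi-square.** With control 25/50/25 and 50 per arm:

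| Valve-less split | Shape | Chi-square | Wilcoxon |
|---|---|---|---|
| 5/70/25 | poor ratings become average only | 77% | 32% |
| 25/25/50 | average ratings become above average only | 75% | 41% |
| 40/20/40 | non-monotone | 83% | 6% |

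**The case against.** The strongest objection is that the power gain comes from the proportional-odds assumption. Step 4 shows two patterns in which the device only helps and yet the chi-square is far stronger. The first, in which the trocar removes the bad cases and does nothing else, is a plausible form of what section 1.2 expects. This stands: the change is a trade-off, and a reader who takes the gain as free would be wrong. It does not make the unordered test the better default. For an ordered rating with a one-way expectation, an ordinal analysis is the standard choice, and it gives the directional estimate that the chi-square does not.

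The plan also asks less about direction than one might suppose. Aim #2 says only that groups will be compared, and the hypothesis in section 2.2 does not mention smoke; the direction comes from the background and the list of potential benefits. The planned percentages by group would also show which way the ratings moved. Both points are fair. What remains missing is a test that uses the order and an effect estimate with its uncertainty.

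A reader might go further and infer that the word *amount* will cause the result to be reported with the wrong sign. The documents do not support that. The item is called evacuation quality throughout, including in the title of the form, so higher is better is the likelier reading. Even amount of evacuation points the same way. Section 2.4 names a single surgeon, who can confirm the meaning, and the data collection forms in the other appendices are not in the text reviewed and may define the coding.

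**Conclusion.** The point holds as a modest improvement to one secondary comparison. The planned chi-square ignores the order of the rating and gives no directional effect estimate. Under the assumed 50 per arm, proportional-odds shift and the three control splits tabulated, it gives up about 9 to 11 points of power for odds ratios of 2 to 3, and about 4 to 5 points at 1.5 or 4. If the effect has another shape, the comparison can reverse by a wide margin. The plan does not say which shape to expect.

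It would be wrong to infer that the planned test is invalid: its type I error is about 5%. The primary observation, PaCO₂, is unaffected. The labelling is a small risk to interpretation and not an expected error.

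**What to change.** In section 2.5, Aim #2, replace the chi-square for smoke evacuation quality with a tie-corrected Wilcoxon rank-sum test or a proportional-odds model reporting an odds ratio with 95% CI, and keep the category percentages by group. The model has the further merit that it can take covariates, which section 2.5 requires if baseline characteristics differ between groups. Name the test before the ratings are seen, because the better test depends on the shape of the difference and must not be picked from the observed table.

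As a minor clarification, in Table 2(b), item 12 and in Appendix B reduce the middle label to *Average* and state that 3 is the best evacuation.

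The cost is one sentence in section 2.5 and one label in two places, with no extra patients or data. The accepted risk is the loss of power shown in Step 4 if the effect crosses only one category boundary or is non-monotone; the retained percentages would let a reader see such a pattern.
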